**List of Abbreviations**

BPD	Bronchopulmonary Dysplasia
CRF	Case Report Form
CRP	C-Reactive Protein
LC-MS	Liquid Chromatography-Mass Spectrometry
LOS	Late-Onset Sepsis
PHI	Protected Health Information
NEC	Necrotizing Enterocolitis
NETs	Neutrophil Extracellular Traps
NICU	Neonatal Intensive Care Unit
PROM	Premature rupture of membranes
RDS	Respiratory Distress Syndrome
ROC	Receiver Operating Characteristic

## Study Summary

Title	Circulating markers in preterm infants with perinatal and neonatal inflammation: an observational study (NEOINFLAM)
Short Title	Markers for perinatal and neonatal inflammation
Study type	Observational study
Study Duration	18 months (October 2017-June 2019)
Study Center(s)	Single Center- Neonatal department, Bao'an Maternal and Child Health Hospital, Shenzhen, Guangdong, China
Objectives	The main objective of the study is to identify new circulating markers associated with early life inflammatory conditions in preterm infants including chorioamnionitis, late-onset sepsis and necrotizing enterocolitis in preterm infants during the first four weeks of life. The aim is to better understand these conditions, and more long-term, to provide earlier and better diagnosis.
Number of Subjects	200
Diagnosis and Main Inclusion Criteria	Inclusion criteria: preterm infants (< 32 weeks of gestation) Main diagnosis before and during the study: chorioamnionitis, late onset-sepsis and necrotizing enterocolitis

# 1 Introduction

This document is a protocol for a human research study. This study is to be conducted according to Chinese medical standards, applicable government regulations and Institutional research policies and procedures.

## 1.1 Background

Every year, approximately 15 million infants are born preterm (< 37 weeks of gestation) and 1 million die (1). Preterm infants, especially those are born < 32 weeks of gestation, have immature gastrointestinal tract and innate immune system, which lead to high risks of development of necrotizing enterocolitis (NEC, a devastating intestinal disease affecting 7% preterm infants) and early life systemic infection (late-onset sepsis, LOS, up to 20-40% all hospitalized infants) (1,2). Those infectious diseases may lead to further long-term complications such as neurodevelopmental delay (1). NEC is very often related to LOS, possibly because an abnormal gut bacterial colonization and high gut permeability allow bacterial translocation (3). Conversely, a systemic inflammatory insult may predispose to NEC via impaired gut motility and immunity. As a result, in clinical trials, diagnostic markers are often used for combined LOS and/or NEC. Despite tremendous efforts to develop diagnostic markers for LOS and NEC, none of them are specific enough for clinical use (4). The current “gold standard” of blood culturing for diagnosis of LOS has many highly false negatives and is time-consuming whereas patients may develop septic shock and die shortly after clinical presentation. Ng et al performed a proteomic study to characterize protein biomarkers for LOS and NEC, but their work was exploratory without detailed focus on the mechanism based on an conventional LC-MS protocols (4). Recently, new mechanisms have been suggested to play role in the pathogenesis of adult sepsis such as circulating neutrophil extracellular traps (NETs), microparticles and miRNA but they have not been characterized in neonatal diseases (5,6).

During pregnancy and labor, 20% of term and up to 60% of preterm deliveries show signs of maternal/prenatal inflammation (7), chorioamnionitis, which is the most important risk factor for preterm birth. Prenatal inflammation is associated with postnatal gut and systemic inflammation in newborn infants (8) and this may affect immune development in several ways. However, no study has yet investigated whether parameters related to postnatal immune development in preterm infants are affected by chorioamnionitis, and how immune parameters in infants with chorioamnionitis are associated with postnatal infections. Further, it is unclear how important the progression of enteral feeding with milk (mother's own milk, donor milk or formula) is for the postnatal NEC and LOS sensitivity. We speculate that early feeding with an optimal milk diet may help to support both gut and systemic immunity development, and thereby increase the resistance against NEC and LOS.

To improve the understanding of NEC and LOS, and their diagnostic criteria, and the postnatal immune development after chorioamnionitis, we investigate temporal blood samples in n=200 preterm infants. We apply proteomics and several immune assays to plasma, as well as whole blood transcriptomics/epigenetics to blood collected from preterm infants with and without NEC, LOS and/or CA. The aim is to identify new proteins and transcriptomic/epigenetic parameters that are related to the mechanisms of NEC, LOS and CA. These biological markers may help to provide possible new diagnostic markers for neonatal LOS and NEC, with and

without maternal chorioamnionitis and with/without difficulties in establishing normal enteral feeding.

### ***1.2 Investigational Agent***

Not applicable

## 2 Study Objectives

[figure not shown]
**Primary objective:** To characterize circulating markers associated with the early life complications including chorioamnionitis, LOS and NEC in preterm infants during the first four weeks of life.

**Secondary objective:** To characterize how different feeding regimes and diets may affect these markers during the first four weeks of life in preterm infants

### 3 Study Design

#### 3.1 General Design

- This observational prospective cohort study includes 200 preterm infants, born < 32 weeks of gestation, at Neonatal Department, Bao'an Maternal and Child Health Hospital, Shenzhen, Guangdong, China.
- Patients, who fulfill inclusion criteria, will be recruited following the parental consent. The recruitment stops when the sample size reaches 200. Expected study duration: January 2017-June 2018.
- Patients will follow usual clinical procedures at the hospital. Patient groups will be categorized based on clinical records: infants born without and with clinical chorioamnionitis, infants without or with at least one episode of late-onset sepsis (LOS) and/or necrotizing enterocolitis (NEC).
- Enrollment and sampling are performed as indicated in the diagram below. Blood sampling is performed every week from birth until 4 weeks of age, or until discharge

#### 3.2 Primary Study Endpoints

- Circulating markers in temporal postnatal blood samples associated with chorioamnionitis.

- Circulating markers in temporal postnatal blood samples associated with prognosis and/or diagnosis of neonatal LOS and/or NEC

### ***3.3 Secondary Study Endpoints***

- Circulating markers in temporal blood samples associated with feeding regimes and diets: major amount of mother's own milk ( $\geq 50\%$  of feeding times during the first two weeks of life as mother's own milk) or minor amount of mother's own milk ( $< 50\%$  of feeding boluses during the first two weeks of life as mother's own milk).

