### 4.3 Subject Recruitment and Screening

When infants are admitted to the Neonatal department, parents are informed about this observational study and the possibility to participate by the principal investigator. Signed parenteral consent is required to enter the study. Subjects should be recruited and the first blood sampling will be performed within the first 48 h of life.

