## 5 Study Procedures

Care of patients follows standard procedures established by the local hospital. Blood samples will be taken according to the study design. At each blood sampling period, the study investigator will evaluate the suitable blood volume to be taken, based on body weight, health status and other guidelines from the hospitals.

Feeding regime follows the practice at the local NICU: mother's own milk is the first priority, followed by donor milk and infant formula. For each time of feeding, the following details are noted in the feeding CRF: time, type of feeding (mother's milk, donor milk, formula), feeding volume, gastric residual from previous feeding. For feeding intolerance, any interventions such as aspiration, decreased the amount of feeding or stop feeding are noted in the comments section of the CRF.

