### **5.3 Sample selection, analysis and comparison**

At the end of the study, the selection of appropriate samples for analysis will be conducted by all investigators of the study. Samples included in the analysis are those collected from birth until the disease diagnosis or completion of 4 postnatal weeks. In case of clinical diagnosis of LOS and/or NEC before completion of 4 weeks, further routine sample collection after diagnosis is continued if feasible.

Temporal samples will be analyzed to perform three separate comparisons:

- Infants without versus with LOS and/or NEC
- Infants without versus with clinical/histological chorioamnionitis
- Infants with major or minor amount of mother's own milk during the first two weeks of life ( $\geq$  or < 50% of feeding times as complete mother's own milk).

Plasma proteomic study will be prioritized and will include as many samples as possible, followed by validation with absolute quantification of potential proteins using immune assays. The type of other -omic analysis for plasma (miRNA profiling) whole blood (transcriptomics or epigenetics) as well as sample size will be decided depending on the results of proteomic study.

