### 6.2 Statistical Methods

Infant grouping will be categorized based on the defined endpoints to compare: 1. Infants with vs. without chorioamnionitis; 2. Infants with vs. without LOS and/or NEC; 3. Infants with vs. without major mother's own milk feeding. Temporal data obtained from -omic analyses of blood and plasma samples collected every week will be analyzed by multivariate analysis with control for false discovery rates. Other data obtained from immune assays will be analyzed by univariate analysis. A panel of potential biomarkers will be identified by regression algorithm together with ROC analysis.

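### The mother's-own-milk groups are set by two weeks of feeding but compared on blood from birth, so a difference at 48 h mostly cannot, and one at day 7 only partly can, be an effect of feeding

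*Protocol*

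**What the plan says.** Section 3.3 splits infants into major and minor groups at 50% "of feeding times during the first two weeks of life as mother's own milk". Section 5.3 repeats the two-week window and the 50% cut.

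Section 5.3 also states which blood samples are used: "Samples included in the analysis are those collected from birth until the disease diagnosis or completion of 4 postnatal weeks". It continues: "Temporal samples will be analyzed to perform three separate comparisons". The milk comparison is the third of these. Section 6.2 lists it again as "Infants with vs. without major mother's own milk feeding", for analysis on the weekly data.

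On timing, section 4.3 says that "the first blood sampling will be performed within the first 48 h of life", and section 3.1 says "Blood sampling is performed every week from birth until 4 weeks of age, or until discharge".

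Section 2 gives the secondary objective as characterising how feeding may affect the markers over the first four weeks. Section 5 describes the feeding order: "mother's own milk is the first priority, followed by donor milk and infant formula". It also has the feeding CRF log when each feed was given and which milk it was.

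No section starts the milk comparison later than birth, ties each sample to the feeding that came before it, or names the first sample as a baseline.

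**The concern.** Exposure should precede outcome. Here the exposure is complete only at day 14, while the outcome is measured from the first two days of life. Early blood is therefore sorted partly by feeds that had not yet been given.

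A difference between milk groups in the first sample would mostly reflect whatever distinguishes infants who go on to receive more or less mother's own milk. Followed as written, the plan could list such a marker as diet-associated. Milk type can change from feed to feed under the section 5 order of priority, so the two-week group need not match the diet an infant had received when an early sample was drawn. The resulting error can go in either direction.

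**Working it through.** The protocol gives no figure to reproduce on this point. Section 6.1 sets the 200 infants on practical grounds, and the question here is one of time order.

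**Inputs from the protocol.** Exposure window: 14 days (3.3, 5.3). Cut: 50% of feeds. First sample: by 48 h (4.3). Later samples: weekly to 4 weeks (3.1), read here as nominal days 7, 14, 21 and 28.

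**Assumptions.** Feeds are evenly spaced, and feeding starts on day s, with s from 0 to 3. The protocol gives neither feed frequency nor the day of first feed.

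**Formula.** Share of group-defining feeding that falls after a sample on day t (for t up to 14) = (14 − max(t, s)) / (14 − s).

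| Feeding starts (s) | 48 h sample (t = 2) | Day-7 sample (t = 7) | Day 14 and later |
|---|---|---|---|
| 0 | 12/14 = 86% | 7/14 = 50% | 0% |
| 1 | 12/13 = 92% | 7/13 = 54% | 0% |
| 2 | 12/12 = 100% | 7/12 = 58% | 0% |
| 3 | 11/11 = 100% | 7/11 = 64% | 0% |

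Since 48 h is the latest time for the first sample, 86% is the lowest value in that column; a sample at 24 h with feeding from birth gives 13/14 = 93%. Two of the five nominal sampling times precede the end of the window.

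**Can the label differ from the diet received so far?** Take equal feeds per day, a = days of mother's own milk in days 1–7, and x = such days in days 8–14. The label rests on (a + x)/14; the diet before the day-7 sample is a/7.

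- a = 3: 3/7 = 43% so far (minor). With x = 4, 7/14 = 50%, labelled major.
- a = 4: 4/7 = 57% so far (major). With x = 2, 6/14 = 43%, labelled minor.
- a = 7: at least 7/14 = 50% whatever follows, so the label cannot change.

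These cases show that relabelling is possible in both directions. They do not show how often it happens.

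**The case against.** The best defence is that comparing two fixed groups on weekly data, first sample included, is ordinary trajectory analysis, and that the 48 h sample usefully shows whether the groups already differed. Section 3.3 speaks only of markers associated with feeding. Section 5.3 leaves the selection of suitable samples to the investigators at the end of the study, and an analysis plan not shown here could add a baseline adjustment or a later start.

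Part of this stands. The protocol does not say that a 48 h difference will be read as an effect of feeding, and using that sample as a baseline is compatible with most of the text. But section 2 asks how feeding may affect the markers, and the one sample rule stated in 5.3 starts at birth and precedes all three comparisons. The protocol itself fixes both windows; the point does not rest on a detail left to another document.

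It is also fair that day 7 is not like 48 h. With feeding from birth, half of the group-defining feeds have been given by then, and 36% to 46% with a start on days 1 to 3. That sample can carry a real effect of feeding.

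A reader might go further and infer that illness drives the grouping: after a diagnosis of LOS or NEC before day 14, later feeds would help to classify pre-diagnosis blood. The window does allow this, but it changes a group only if feeding continues or resumes with a milk mix that crosses 50%. The protocol gives neither the timing of onset nor the feeding that follows diagnosis, so this remains a possibility and not a demonstrated fault.

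Section 5.3 counts feeds "of feeding times as complete mother's own milk" where 3.3 omits the word complete. That is a clerical difference and has no bearing on timing.

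**Conclusion.** The point holds for the secondary milk comparison and should be corrected. Grouping by feeding over days 0 to 14 is out of time order for the first sample (86% to 100% of the group-defining feeding still to come) and partly so for the day-7 sample (50% to 64%). These ranges rest on even feeding, a start between birth and day 3, and the nominal visit days. Samples from day 14 onward are sound in this respect.

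The documents do not support the view that the whole milk comparison is invalid, or that the chorioamnionitis and LOS/NEC comparisons are affected by this timing. Nor do they allow a count of misgrouped infants. Section 6.1 expects LOS and/or NEC in 20–30% (40 to 60 of 200), but without onset times or feeding patterns that does not yield a number affected.

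**What to change.** In sections 5.3 and 6.2, for the milk comparison only:

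1. Treat the sample taken within 48 h as baseline, for example as a covariate, and not as an outcome of feeding.
2. Analyse the day-7 sample by the share of mother's own milk among feeds given before it, keeping the 50% cut.
3. Keep the fixed two-week grouping for samples from day 14 onward, and state that these come only from infants not yet diagnosed and still in hospital.

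The cost is wording and one derived variable, built from feed times and types already in the feeding CRF. No new blood, data or change in feeding is needed. There are real drawbacks: the day-7 share rests on fewer feeds, it is undefined for an infant not yet fed, and an infant's day-7 group may differ from its two-week group, so the display is less simple than a single two-group plot.

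### The only feeding exposure is cut into two groups at 50% of feeds; under a linear relation this discards roughly 11% to 55% of the information in a share that planned data already provide

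*Protocol*

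**What the plan says.** The secondary objective (Protocol, Section 2) concerns how feeding regimes and diets affect the circulating markers. Three places define the exposure for it:

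- **Section 3.3** sets the *major* group at 50% or more "of feeding times during the first two weeks of life as" mother's own milk and the *minor* group at less than 50% "of feeding boluses during the first two weeks of life as mother's own milk".
- **Section 5.3** repeats the cut as a share "of feeding times as complete mother's own milk".
- **Section 6.2** lists it as a comparison of infants with and without major mother's own milk feeding.

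No continuous version appears, and no reason is given for 50%. Section 5 says that the feeding CRF holds, for each feed, "time, type of feeding (mother's milk, donor milk, formula), feeding volume, gastric residual from previous feeding". Section 6.1 sets the cohort at 200 infants on practical grounds.

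**The concern.** A proportion that can be calculated for every infant is reduced to a yes/no variable before any marker is analysed. Differences within each group, such as 0% against 49%, are ignored, and a trivial difference across the cut is treated as the whole contrast. If a marker changes gradually with exposure, this lowers power for the secondary objective. Cohort size is tied to admission rate and sampling capacity, so the loss cannot readily be made up by recruiting more infants.

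Two lesser matters concern the definition itself. It is labelled an amount ("major amount of mother's own milk") but counts feeds, so a small feed weighs as much as a large one. Section 5.3 also adds the word complete, which Section 3.3 lacks, and Section 5 lists three feed types with no category or rule for a mixed feed.

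**Working it through.** **No plan figure to reproduce.** The protocol gives no alpha, power, effect size or expected split for the feeding comparison. The 200 in Section 6.1 is a feasibility figure.

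**Information kept by the cut.** If a marker is linear in the share *x*, the efficiency of the two-group analysis relative to the continuous one is the squared correlation between *x* and the indicator *d* = 1 when *x* ≥ cut, and 0 otherwise.

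For a normal exposure with a proportion *p* in one group, efficiency = φ(z_p)² / [p(1−p)]:

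- p = 0.5: 0.3989² / 0.25 = 0.637 (= 2/π), loss 36%; 200 infants act like 200 × 0.637 ≈ 127.
- p = 0.3: 0.576, loss 42%.
- p = 0.2: 0.490, loss 51%.

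The actual exposure is a share bounded by 0 and 1 and cut at 0.5. For a uniform share the result is exact: covariance = 3/8 − 1/4 = 1/8, Var(*x*) = 1/12, Var(*d*) = 1/4, so efficiency = (1/64) / (1/48) = 0.75. The other shapes are assumed beta distributions, with 1,000,000 simulated draws each:

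| Assumed shape of the share | In major group | Efficiency | Loss |
|---|---|---|---|
| Strongly U-shaped, beta(0.2, 0.2) | 50% | 0.891 | 11% |
| U-shaped, beta(0.5, 0.5) | 50% | 0.810 | 19% |
| Skewed U, beta(0.3, 0.6) | 31% | 0.813 | 19% |
| Uniform | 50% | 0.750 | 25% |
| Single peak, beta(2, 2) | 50% | 0.703 | 30% |
| Triangular, beta(2, 1) | 75% | 0.667 | 33% |
| One-sided, beta(3, 1) | 88% | 0.536 | 46% |
| Very one-sided, beta(2, 5) | 11% | 0.450 | 55% |

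These are scenarios, not bounds.

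**What this means for power.** Assume all 200 infants are analysed, one marker, two-sided alpha 0.05, a true correlation of 0.20 and a linear relation. By the Fisher approximation, power = Φ(arctanh(0.20 × √efficiency) × √197 − 1.96):

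- continuous share (efficiency 1): 81%
- strongly U-shaped (about 0.90): 77%
- uniform (0.75): 69%
- normal, median split (0.637): 62%

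**Count share against volume share.** Assume the same number of feeds each day for 14 days and a feed volume that rises linearly 10-fold, from 1 to 10 units. One feed per day over 14 days then totals 14 × 5.5 = 77 units.

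- Mother's own milk only from day 9: 6/14 = 43% of feeds (*minor*), but 49.6/77 = 64% of volume.
- Mother's own milk only through day 8: 8/14 = 57% of feeds (*major*), but 27.4/77 = 36% of volume.

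With a 5-fold rise the volume shares are 60% and 40%. With constant volume the two measures agree.

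**Mixed feeds.** An infant whose every feed mixes mother's own and donor milk could score 100% under one reading of Section 3.3 and 0% under Section 5.3.

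**The case against.** The loss depends on a distribution that nobody has stated, and a small loss is plausible. Section 5 gives mother's own milk first priority with donor milk and formula as fallback, so shares may pile up near the extremes, where the cut costs least. If the biology is a step at 50%, the cut is the right model and a linear term is the worse one. The comparison is secondary and exploratory, and Section 6.1 claims no power that could be eroded. Section 5.3 also leaves sample selection to the end of the study, so the number analysed may not be 200. A continuous analysis could be added in a statistical analysis plan, and the raw feed data allow it. All of this stands, and it keeps the point small.

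Counting feeds can also be defended. Section 3.3 spells out its definition, so no reader is misled by the label. Section 1.1 stresses early feeding; if volumes rise, a volume share gives those early feeds less weight. Section 5 notes that feeds may be reduced or stopped for intolerance, which would influence a volume share more. These arguments stand against making volume the main exposure. They do not favour a two-group cut over a continuous count share.

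The reference to a later analysis plan does not remove the point, because the protocol itself fixes the two-group form in three sections and offers no other feeding exposure.

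**Conclusion.** The point holds as a modest improvement. The plan discards part of a share that it can already compute. If a marker is linear in that share, the loss runs from about 11% to 55% over the bounded shapes examined, with 25% for a uniform share; it is 36% for a normal exposure split at the median. It is nil if the true effect is a step at 50%.

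Three stronger readings are tempting, and the documents support none of them:

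- **That more than a third of the information is lost, or at best some 70 of 200 infants.** The 36% (200 × 0.363 ≈ 73 infants) needs a normal exposure as well as linearity. A uniform share costs about 50 infants, and the symmetric U-shapes tabulated about 22 to 38.
- **That counting feeds misclassifies infants and volume must replace it.** No section makes volume the standard. The reversals shown above need an assumed rise in feed volume.
- **That Section 3.3 contradicts itself by using feeding times for one group and boluses for the other.** These are most naturally two words for a feed, so this is a matter of wording. The word complete in Section 5.3 matters more, because it can change how a mixed feed counts.

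**What to change.** In Sections 3.3, 5.3 and 6.2:

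- Make the continuous share of feeds given as mother's own milk over the first two weeks the main exposure for this comparison, as a linear or spline term chosen before the marker data are examined.
- Keep the 50% split for description.
- Add the volume-based share from the feeding CRF as a sensitivity analysis.
- Use one term for a feed. State whether only feeds that are wholly mother's own milk count, and apply that rule in both 3.3 and 5.3. The volume share needs a mixed-feed rule too.

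The cost is two derived variables from data already planned, with no extra blood and no change in care. A functional form has to be assumed, and a slope or curve is slightly harder to present than two groups. A spline relaxes the linear assumption but spends degrees of freedom, so it recovers somewhat less power than the linear figures above suggest.
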